5.0 Study Design and Statistical Analysis Plan

5.1 *Describe the basic study design/approach (e.g., qualitative study using five focus groups of first year students to describe assimilation into the university community; randomized controlled trial of a behavioral change intervention to increase dietary intake of whole grains; pre- post-test evaluation of new pedagogical techniques to improve adult literacy):*

The pilot study will be a within-subjects design used to compare ratings of beverages with different levels of sweetness provided by different sugars and non-nutritive sweeteners (see 7.0:Investigational Agents: Beverage Solutions, below, for ingredients).

The overall study will be a within-subjects (crossover) design used to compare behavioral (beverage ratings and preferences), metabolic (blood glucose & metabolites, indirect calorimetry measures), and brain activation responses (fMRI) to glucose-, fructose-, and sucrose-containing beverages (Aim 1); and sucrose-, high fructose corn syrup (HFCS)-, and non-nutritive sweetener + sucrose- containing beverages (Aim 2).

5.2 *Describe corresponding data analysis plan/approach (e.g., content analysis of focus group transcripts; descriptive analysis followed by linear regression modeling; nonparametric analysis of pre- and post-test measures):*

Linear mixed effects models will be used to assess the following outcome variables: change in indirect calorimetry measures, change in blood glucose and insulin, change in beverage liking. Linear regression will be used to relate blood and indirect calorimetry measures to liking and other subjective ratings.

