Participants will be trained on how to use standard perceptual rating scales used in the study. Then, they will taste, rate, and rank each mixture using these scales. All mixtures will be within common sweetness concentrations found in commercially available beverages (i.e., we will not provide sugar or non-nutritive sweetener amounts that would commonly cause gastrointestinal discomfort in most people). Data from this pilot study will then be used to determine acceptable concentrations of sugars and non-nutritive sweeteners to be used in the full study.

FULL STUDY:

OVERVIEW:

Approximately 200 participants will be recruited from the general public for this randomized crossover study conducted at the FBRI. Our goal is to have approximately 140 participants complete the study. The duration of participation will be no more than 6 weeks for each aim. The figure above depicts the overall study design and procedures for both Aims 1 and 2. The study design is the exact same for Aims 1 and 2, but the beverages selected for conditions "CS1, CS2, and CS3" are different, depending on aim. For Aim 1, conditions will include fructose, glucose, and sucrose. For Aim 2, conditions will include sucrose, high fructose corn syrup (HFCS), and non-nutritive sweetener+sucrose. Each CS drink will be consumed over a 1-week period in sequential weeks without "washout" weeks in between.

Recruitment and Screening:

Approved study recruitment materials will be distributed in the following ways. Flyers will be posted on bulletin boards and approved posting sites throughout Roanoke, Blacksburg, and surrounding areas. Digital advertisements will be displayed on [name] lab and CHBR social media, VT News, and in list serves with permission. All advertisements will include a link to the lab website where there will be approved language describing the research study. Interested participants will fill out a general screening survey. All screening surveys will be delivered through Ripple (a HIPAA-compliant, secure database software; see section 9.4 for description). This screening survey will be used to determine study eligibility. Once the general screening survey has been completed, participants who may be eligible for this study will be contacted via email (see attachment 'Screening email'). If participants choose to complete the study-specific screening form and are eligible for this study, they will be contacted to schedule a consent session.

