CONSENT SESSION (Called "pretest" in study design figure above) (~2.5 hours):

Informed Consent

Participants will be sent via email the consent form for the study at least 24 hours in advance of their scheduled consent session. Upon arrival for the session, participants will have ample time to review and sign the consent form prior to beginning the training session. Research personnel will be available to answer any questions the participant may have.

Anthropometrics and Clinical Measures

Participants' height, weight, hip circumference, and waist circumferences will be measured. Height will be measured using a stadiometer, weight using a body weight scale, and waist and hip circumference using a standard Gulick tape measure. A fingerstick blood sample will be collected for point-of-care hemoglobin A1C assessment to ensure eligibility. A lancing device and single-use lancet will be used to obtain a finger stick. A point-of-care A1C analyzer and appropriate cartridges will be used to assess hemoglobin A1C.

Flavor Ratings

The participants will first be trained by the researcher on how to use the standard perceptual rating scales. Then participants will taste and make ratings of beverages using the standard rating scales. After the participant has completed the tasting protocol, the researcher will determine three flavors to be used in the beverages the participants will consume during the behavioral conditioning sessions.

Mock MRI Training

Participants will also complete a "mock" MRI training, in which they learn to swallow small amounts of liquids while lying supine. (Note: most people have no difficulty learning to swallow small quantities of liquid while lying down). This training will be performed in an MRI simulator that is the same bore size and similar environment to the real scanner, but does not contain a magnetic field. Participants who have difficulty with supine swallowing or who express discomfort in the simulated fMRI environment may be excluded from the study or only undergo portions of the study that do not involve fMRI scanning. If not completed during the consent session, participants will be asked to complete this training as part of another conditioning session. Compensation for this "mock" scan is built into the compensation for the consent session.

Dietary Intake

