Fast and Refrain from Exercise

Participants will be asked to refrain from exercise for at least 24 hours and fast for 3 hours prior to each conditioning session.

Internal State Ratings

Participants will rate their hunger, thirst, and fullness on standard visual analog scales while fasted and periodically throughout the session.

Flavor Ratings

Participants will taste and make ratings of flavored beverages using standard rating scales. These are the same beverages and flavors used throughout the study.

MRI Scan

The MRI scan will occur at the Human Neuroimaging Laboratory at FBRI. MRI safety will be reviewed with the participant by an FBRI-approved scanner operator prior to entering the scanner room containing the magnet. Participants and experimenters will remove metal from their bodies and clothing (e.g., jewelry, cell phones, coins, etc.). Participants will also complete an MRI safety form to ensure they qualify to have an MRI performed (included in supporting documents). Prior to entering the scanner room with

the magnet, experimenters will use a metal detection wand to scan over the participant to ensure no metal that could be subject to the magnet's pull is detected (e.g., zippers or grommets on clothing cannot be pulled off by the magnet). Inside the scanner room, participants will lie on a table that slides into the bore of the scanner. Using a head coil, functional images will be acquired using an EPI bold sequence. Participants will wear disposable earplugs and other ear protection to minimize the amount of noise heard during the scan (magnetic field gradient changes during the scan can be loud).

Participants are able to communicate with the experimenter via either a speaker and microphone system (between scanning segments) or with an emergency squeeze ball (during scan acquisition). Participants will be instructed to talk with experimenters between scanning segments via microphone-and-speaker system and to use the squeeze ball during scan acquisition for emergencies (e.g., they begin to feel claustrophobic during the scan). The experimenters will check in with participants periodically between scanning segments to ensure participant comfort.

Scanner Taste Tasks

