14.0 Number of Subjects

14.1 Indicate the total number of subjects to be enrolled and how this number was determined (e.g., sample size calculation [show], number of available subjects in a finite pool, number of tests funding award would allow):

For the pilot study, we plan to consent 25 participants with the intent of having 20 complete the pilot study session.

For the full study, we plan to consent approximately 200 participants with the intent of having 70 participants complete Aim 1 and 70 participants complete Aim 2. These numbers were determined using power calculations based on other studies with similar designs conducted by our lab. We anticipate ~30% rate of either drop-out or exclusion after enrollment (e.g., unable to determine flavors equally liked and unfamiliar for the conditioning paradigm, hemoglobin A1C outside of the inclusion range, scheduling challenges, etc.).

14.2 If this is a multi-site study, indicate the number of subjects to be enrolled at this site and the total to be enrolled from all sites:

Single site

14.3 If applicable, indicate the number of potential subjects you expect to screen for enrollment, and the number of subjects you will need to complete the research procedures:

For the pilot study, we anticipate screening via the online screening process approximately 25 potential participants. We anticipate enrolling and screening approximately 20 participants during the Consent Session. We intend to have 20 participants complete the pilot study.

For the full study, we anticipate screening via the online screening process approximately 2000 potential participants. We anticipate enrolling and screening approximately 200 participants during the Consent Session. We intend to have 70 participants complete Aim 1 and 70 participants complete Aim 2. We anticipate that a majority of these participants will complete only 1 aim; however, it is possible and allowable for participants to complete both aims if they qualify for both (i.e., at least 6 flavors are rated as equally liked and equally unfamiliar in the Consent Session).

14.4 If the study has more than one procedure, indicate the total number of subjects to undergo each procedure separately:

Pilot Study (single session for each sweet mixture): 20 participants

Full-Study

Consent Session (flavor tasting/rating, anthropometrics, fingerstick sample for HbA1C): 200 participants

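### Liking is rated before and after conditioning, but section 5.2 uses the pretest rating at most by subtraction and does not say how it enters the regression on metabolic measures

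*Combined protocol and SAP*

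**What the plan says.** Section 5.2 contains two analysis sentences. The first lists the mixed-model outcomes: "change in indirect calorimetry measures, change in blood glucose and insulin, change in beverage liking". The second covers the link between metabolism and reward: "Linear regression will be used to relate blood and indirect calorimetry measures to liking and other subjective ratings". Neither names a pretest covariate. The second also leaves open which liking rating is used, at which time point, which variable is the response, and whether there is a participant term.

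A baseline rating is collected. At the consent session, which section 8.2 also labels the pretest, "Then participants will taste and make ratings of beverages using the standard rating scales". Section 14 shows that liking is among those ratings: entering both aims requires that "at least 6 flavors are rated as equally liked and equally unfamiliar in the Consent Session", and one example of exclusion after enrollment is "unable to determine flavors equally liked and unfamiliar for the conditioning paradigm". At post-test "Participants will taste and make ratings of flavored beverages using standard rating scales", and "These are the same beverages and flavors used throughout the study". Section 8.2 calls the design a "randomized crossover study conducted at the FBRI", with three beverages per aim. Section 14.1 plans 70 completers per aim.

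**The concern.** Beverage ratings are among the primary endpoints (section 4.1), and section 3.3 rests the study on post-ingestive signals being linked to reward learning. Of the analyses in 5.2, only the regression ties metabolic signals to liking. Liking at post-test is prior liking plus whatever was learned. Matching flavors within a person does not equalize liking, or use of the rating scale, between people. If a regression across participants uses post-test liking alone, those stable differences remain in the error. If they are related to metabolic response, they also enter the slope.

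The mixed model raises a smaller issue of efficiency. Subtracting the baseline fixes its coefficient at 1, whereas a covariate lets the data set it.

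**Working it through.** **The plan's own figures.** The 70 per aim cannot be reproduced, because 14.1 shows no alpha, power, effect size or SD. The enrollment step does reproduce: 140 / (1 − 0.30) = 200.

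**Assumed inputs.** Two-sided alpha 0.05; 80% power before adjustment in step 1; pre-post correlation of liking ρ = 0.5 (range 0.3 to 0.7); correlation g between pretest liking and metabolic response from 0 to 0.3; n = 70. The documents give only the 70.

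**1. Mixed model comparing beverages.** Scale unrestricted pretest and post-test ratings to unit variance, and let k be the share of within-person baseline variance left after flavor matching. The error variance is (1 − ρ²) with the covariate and (1 − ρ²) + (1 − ρ)²k with subtraction. At ρ = 0.5 the ratio is 0.75 / (0.75 + 0.25k). The noncentrality for 80% power (2.842, 68 df) is divided by the square root of that ratio, with 67 df:

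| k | variance ratio | power with covariate |
|---|---|---|
| 1 | 0.750 | 90% |
| 0.5 | 0.857 | 86% |
| 0.25 | 0.923 | 83% |
| 0.1 | 0.968 | 81% |

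A simulation gave 89%, 85%, 82% and 80%, with type I error near 5%. At k = 1 the formula gives 93% for ρ = 0.3 and 86% for ρ = 0.7; at k = 0.25 it gives 85% and 82%.

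**2. Power of the regression, one value per participant, g = 0.** With an assumed true correlation r = 0.30 between metabolic response and post-test liking, Fisher-z power is 71.7% unadjusted. The effective correlation becomes r/√(1 − ρ²) with the covariate and r/√(2 − 2ρ) with a change score. For ρ = 0.3, 0.5 and 0.7:

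- covariate: 75.3%, 83.5%, 95.3%
- change score: 56.4%, 71.7%, 91.7%

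**3. False positives in the regression when nothing is learned.** Two structures are plausible.

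- *A: metabolic response tracks the pretest rating itself.* Its correlation with post-test liking is gρ, with the change score −g√((1 − ρ)/2), and with post-test liking given the covariate 0.
- *B: metabolic response tracks a stable trait (general liking or scale use) that both ratings measure with independent error.* The correlations are g with post-test liking, 0 with the change score, and g(1 − ρ)/√((1 − g²)(1 − ρ²)) given the covariate.

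The rejection rate is Φ(t − 1.96) + Φ(−t − 1.96), where t = atanh(correlation) × √67 (√66 with the covariate). At ρ = 0.5:

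| structure, g | post-test level | change score | pretest covariate |
|---|---|---|---|
| either, 0 | 5% | 5% | 5% |
| A, 0.2 | 13% | 13% | 5% |
| A, 0.3 | 24% | 24% | 5% |
| B, 0.2 | 38% | 5% | 16% |
| B, 0.3 | 72% | 5% | 32% |

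Simulations agree within about two points. At g = 0.3, moving ρ from 0.3 to 0.7 takes the level under A from 11% to 42%, the change score under A from 31% to 16%, and the covariate under B from 48% to about 19%. At g = 0.1 and ρ = 0.5, the level is rejected in 7% (A) or 13% (B).

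If choosing flavors from a narrow liking band also cut the pretest variance between people to a quarter, the simulated level figure under A at g = 0.3 falls from 24% to 6% (ρ = 0.5) and from 42% to 9% (ρ = 0.7).

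**The case against.** **The regression may already use change.** A reader might infer that 5.2 commits to the raw level of liking. The text does not establish that. The regression sentence drops the word change from the blood and calorimetry measures as well as from liking, so it may be shorthand for the outcomes just listed. It may also refer to ratings taken in the conditioning sessions, alongside that session's metabolic response. Nor does 5.2 say that change in liking is measured from the consent session. This stands: the plan is silent rather than wrong. The silence still has to be resolved, since under structure A a change score fails as well.

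**The design protects the beverage comparison.** A reader might infer that prior liking can pass for learned liking throughout the trial. It should not do so in the comparison that tests the hypotheses in 2.2, because the crossover is randomized and flavors are matched within each participant. This stands. The exposure is confined to a regression across participants with no participant term. Change scores in the mixed model are valid, and the covariate only improves their efficiency, by little if matching is tight.

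**The covariate is not a cure.** A reader might infer that adjusting for pretest liking removes the confounding. It does under structure A. Under structure B one rating measures the trait with error, and subtraction does better. The documents cannot say which structure applies. This stands too. In these calculations, however, ignoring the baseline was never better than both alternatives.

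**Conclusion.** The point holds as a request for a modest improvement and a clarification. In the mixed model, a pretest covariate in place of subtraction is a nearly free gain. Power of 80% rises to at most about 90% at ρ = 0.5, and to about 82-86% if matching leaves a quarter to a half of the within-person baseline variance. This takes the randomization to cover which flavor is paired with which beverage.

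In the regression, unadjusted post-test liking across participants should be ruled out. The size of any confounding depends on ρ and g, which the documents do not give, and is nil at g = 0. Neither the covariate nor the change score is safe alone, because metabolic response is measured and not assigned. The documents do not support saying that the plan definitely analyses raw liking, that the beverage comparison is biased, or that one covariate settles the matter.

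**What to change.** In 5.2:

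1. For the mixed model comparing beverages, make post-test liking of each beverage the outcome, with that participant's pretest liking of the same flavor as a covariate.
2. For the regression, state the liking variable, its time point, the response variable and how the three beverages per participant are handled. Do not use unadjusted post-test liking across participants. Include pretest liking as a covariate and report, as a sensitivity analysis, either the change-score version or a within-participant analysis with a participant term. If the results disagree, present the association as open to confounding by prior liking.
3. State that the baseline is the consent-session rating, and whether the beverages tasted then had the same sugar content as the conditioning beverages.

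The cost is a few sentences in 5.2 and one degree of freedom per model, plus the sensitivity analysis. Both ratings are already collected, so no visit or procedure changes.

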6.0 Setting

6.1 *Describe the sites or locations where your research team will conduct the research. Consider each of the items listed below:*

- *Identify where your research team will identify and recruit potential subjects.*
- *Identify where the team will perform the research procedures.*

- *Describe the composition and involvement of any community advisory board(s).*
- *For research conducted in other locations, describe:*
 - *Site-specific regulations or customs affecting the research at those locations.*
 - *Local scientific and ethical review structure at those locations. Examples include work in other cultures or ethnic groups (within or outside of the U.S.) and work with churches. The HRPP will provide additional guidance for international research.*

Pilot Study:

A convenience sample of individuals will be recruited through word-of-mouth, posted flyers, social media, and other recruitment avenues. Individuals who are willing and able to come to the Center for Health Behaviors Research (CHBR) at the Fralin Biomedical Research Institute (FBRI) will be invited to participate. All study procedures for the pilot study will be conducted at the CHBR at FBRI.

Full Study:

Recruitment will be done through flyers posted in the local community and social media posts. Both avenues of participant recruitment will include information about the study as well as contact information (i.e. email and phone number) for the study and instructions to access the screening survey. Individuals within our Ripple (HIPAA-compliant, see information below in section 9.4) database who have previously indicated they would like to be considered for future studies will also be contacted.

The study procedures for the in-person visits will all take place at the Fralin Biomedical Research Institute (FBRI) at VTC in Roanoke, VA. The consent session will occur at the Center for Health Behavior Research (CHBR) at the FBRI or in metabolic core space in Riverside 4 at the FBRI at VTC. Indirect calorimetry blood draw sessions will occur in the metabolic chamber at the FBRI at VTC. The MRI scan will take place in the Human Neuroimaging Lab (HNL) at the FBRI.

7.0 Study Intervention(s)/Investigational Agent(s)

7.1 Describe the study interventions (including behavioral interventions) and/or investigational agents (e.g., drugs or devices) to be used in this study. Consider each of the items listed below:

- *Drug/Device Handling: If the research involves drugs or devices, describe your plans to store, handle, and administer the drugs or devices so that they will be used only on subjects, and only by authorized investigators.*

- *Describe whether any of the following will be used: microwaves, X-rays, DEXA scans, general anesthesia, or sedation*
- *If control of the drugs or devices used in this protocol will be accomplished by following an established, approved organizational SOP (e.g., Research Pharmacy SOP for the Control of Investigational Drugs, etc.), please reference the SOP in this section.*

Beverage Solutions:

Participants will consume different beverages and "tasteless" solutions at different times throughout the study. Ingredients used in the solutions include: food-grade table sugar, high fructose corn syrup, dextrose, fructose, -non-nutritive sweeteners that are commonly found in the US food supply, citric acid, potassium chloride (a common salt), and sodium bicarbonate (baking soda). Beverages will also include flavors and food coloring commonly used in commercial food products.

All ingredients are common food additives that nearly every participant would have consumed previously in their normal diet.

Device Handling:

This research involves the use of a metabolic chamber which is located in a restricted space requiring proxy access. The MRI scanner involved in this work is located in a restricted, proxy access behind biometrically secure doors

7.2 *List the name of all drugs (including any vitamins, supplements, herbs, or nicotine) to be used in the study. Indicate whether they have FDA approval, and list any limitations for their use:*

No drugs or supplements will be used in the study.

7.3 *List all devices, how they will be used, their purpose in the study, and if they will be used in a manner consistent with their approved uses. If they will be used in ways that are not yet FDA approved, indicate whether they need an IDE or a determination that they are exempt from the IDE Determination. If a determination of significant risk or non-significant risk is needed for any of the devices, include the researcher's recommendation for each of those devices:*

Magnetic Resonance Imaging: Participants will receive an MRI scan. The Siemens 3T scanner has been approved by the FDA and will be used in a manner consistent with approval.

Metabolic Chamber: Participants will undergo metabolic measurements in a metabolic chamber in a manner consistent with approved uses.

7.4 *If the drug is investigational (has an IND) or the device has an IDE or a claim of abbreviated IDE (non-significant risk device), include the following information:*

- *Identify the holder of the IND/IDE/abbreviated IDE.*
- *Explain procedures followed to comply with sponsor requirements for FDA regulated research for the following:*

FDA Regulation	Applicable to:		
	IND Studies	IDE studies	Abbreviated IDE studies
21 CFR 11	X	X	
21 CFR 54	X	X	
21 CFR 210	X		
21 CFR 211	X		
21 CFR 312	X		
21 CFR 812		X	X
21 CFR 820		X	

N/A

